4.0 COHORT STUDY DESIGN

4.1 Overview

The OAI cohort study is a multi-center, longitudinal, observational study focusing primarily on knee osteoarthritis (OA). The study will create a public archive of data, biological samples, and joint images collected over time from a very well clinically characterized population of individuals comprised of two subgroups, 1) those with clinically significant knee OA who are at risk of disease progression and 2) individuals who are at high risk of initiation of clinically significant knee OA.

As originally designed, up to 5,000 age-eligible women and men will be recruited and enrolled at four recruitment centers (the University of Maryland and John's Hopkins comprise a single recruitment center). The baseline assessments consist of an initial eligibility assessment by telephone, a screening clinic visit and an enrollment clinic visit. There will be four annual follow-up visits at which many of the baseline measures will be repeated.

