Similarly, dichotomous outcomes might be modeled using a logistic function with random slopes and intercepts and fit using a nonlinear mixed model program such as SAS Proc NLMIXED (SAS, Version 8). Time-to-event variables, such as incident symptomatic OA, could be analyzed using the discrete-time Cox proportional hazards model with time-varying covariates (a GEE version of this model would be used for knee-based analyses). Predictors of interest might include terms like cartilage volume and possible confounders, or effect modifiers, such as gender. The assumption of proportional hazards can be assessed by including interactions with time and functions of time.

In practice, it is likely there will often be competing candidate surrogate markers each correlated to a different degree with the endpoint. The preferred surrogate is one that is biologically defensible and most highly correlated with the endpoint. The statistical significance of the differences between correlations can be evaluated using a parametric bootstrap.(137)

8.2.4 Expected Rates of Knee OA Incidence and Power for Analyses of Incident Disease

Table 8.1 shows the number of subjects and knees that are expected to develop incident symptomatic knee OA during four years of follow-up in the Incidence subcohort. For the purpose of these estimates, incident symptomatic knee OA is defined as the first occurrence in a knee of frequent knee symptoms (pain, aching or stiffness on most days of at least one month during the past 12 months) and definite tibiofemoral osteophytes in the same knee. Expected incidence is estimated by applying age and gender-specific incidence rates, derived from analyses modeling enrichment of the cohort using risk factors (See Appendix B for details), to the original goals for enrolled subjects in each gender and age stratum (Appendix A). The base age- and gender-specific incidence rates used in the cohort enrichment modeling are taken from published estimates from the Fallon Community Health Plan(35) and the Framingham study.(20, 22) Cumulative loss to follow-up is assumed to be 28% by the end of year 4; 10% dropout at the first follow-up visit and 7% additional dropout in each year after that. Similar calculations are used to estimate the expected number of incident knees, taking into account the ratio of bilateral to unilateral incidence from the Framingham study (unpublished).

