The overall incidence of symptomatic knee OA expected among subjects selected for the OAI Incidence subcohort is 1.8/100 person-years in men and women combined. Adjusted age-specific risks range from about 1.0/100 p-y at age 45-49 to about 2.0/100 p-y in those age 60 and over and are similar by gender. This compares with an observed range in age-specific risks of about 0.2/100 p-y to

0.8/100 p-y in the general population in the same age strata.(35) Cumulative incidence after 4 years is expected to be about 5.5%.

It is likely that these are conservative estimates. The increased risk in the overweight groups derived from the cohort enrichment modeling suggest a smaller effect of weight than is seen in the existing incidence studies. In the Fallon Health Plan, women (mean age 60) who weighed 175 lbs or more had a 5 to 6 fold increased risk of incident clinical knee OA compared to those who weighed less.(138) In the Bristol cohort, men and women in the highest third of BMI (≥ 25.4 kg/m2) had at least a 9-fold higher risk of developing knee OA than those in the lower third.(15) This compares to a risk ratio of 2.0 for prevalent symptomatic knee OA in the upper third of weight in Framingham women and 1.6 for the upper third of weight in men (Appendix B).

Most participants in this subcohort will have two knees at risk for incident disease, and consistent with this the number of knees with incident symptomatic OA (Table 8.1) is projected to be greater than the number of incident case subjects.(20) (and unpublished data) In addition, contralateral knees in the Progression subcohort that are free of prevalent disease at baseline have a high risk of developing OA(139) and may be pooled with cases from the Incidence subcohort for some analyses.

	Subjects with	Knees with
Gender/	Incident Sx OA	Incident Sx OA
Age stratum	Ν	N (%)
Men age 45-69	73	121 (32%)
Men age 70-79	37	62 (17%)
Men age 45-79	110	183 (49%)
Women age 45-69	76	127 (34%)
Women age 70-79	37	61 (17%)
Women age 45-79	113	188 (51%)
All subjects	223	371 (100%)

Table 8.1 Expected number of cases of incident symptomatic knee OA based on enrollment goals in the Incidence subcohort

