Incident radiographic OA (the first occurrence of tibiofemoral osteophytes in knees free of this finding at baseline) is another potential endpoint of interest in this subcohort. The age- and gender-specific incidence of radiographic knee OA, without taking knee symptoms into account, is expected to be about 2.3 to 2.6 times greater than the incidence of symptomatic knee OA.(20) Assuming that one-third of subjects in the Incidence subcohort will already have radiographic knee OA at baseline in at least one knee, over 550 knees are expected develop incident radiographic OA during follow-up.

Occurrence of incident symptomatic OA for knees in the same subject is correlated, so the equivalent number of independent incident knees is smaller. To reflect this, the projected number of incident knees is divided by 1 plus the interclass correlation coefficient to obtain the equivalent number of independent knees.(140) Using the 0.4 interclass correlation for prevalent symptomatic knee OA in the Framingham cohorts, the equivalent of 265 independent knees with incident symptomatic OA is expected by the end of the fourth year of follow-up.

Table 8.2. Power for dickof incident Sx OA obta	L
Exposure	Relative Risk
Prevalence	detectable with
(%)	80% power
50	1.43
33	1.45
25	1.49
10	1.70

Based on expected numbers of endpoints using the original study design assumptions, the power to detect relative risks (RR) between exposed and nonexposed subjects in the Incidence subcohort is displayed in table 8.2. The smallest detectable RR by Cox regression of time to incident OA using a two-sided 0.05 hypothesis test with 80% power is given for dichotomous exposures of 10%, 25%, 33% and 50% prevalence in the table. (In reality, incident cases will accrue on an annual basis and would be analyzed

using a grouped failure time model.)

Figure 8.2 shows the power curves by smallest detectable RR value for each of these exposure prevalence values. Detectable relative risks will be smaller for more common endpoints, such as incident radiographic OA.

Figure 8.2

OAI Power for Incidence of Symptomatic Knee OA

Analyses of structural biomarkers for incident OA will use only the knees from the nested case-control sample, which will have full marker information. (A similar approach will likely be applied to analysis of biochemical markers and incident OA.) Table 8.3 shows relative risks that could be detected in a

Table 8.3 Power for dic of incident Sx OA in c	-

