Exposure	Relative Risk
Prevalence	detectable with
(%)	80% power
50	1.56
33	1.57
25	1.62
10	1.91

nested case-control analysis using an MRIderived risk factor or a biochemical marker as a predictor of time to incident OA. For this it is conservatively assumed that image or biochemical marker data would be available from about 300 case knees and 1200 control knees. Because the number of cases and controls is reduced in the case-control analysis, the detectable relative risks are larger. Even for exposures with 10% prevalence, there is 80% power to detect a relative risk of 1.62 in all subjects, and 1.91 in the case-control analyses.

Analysis of the association of biomarkers with incident OA to evaluate surrogacy, in the case-cohort sample with full biomarker data, might consider the correlation between the time trend in the biomarker with time trend in log odds of incident OA from a logistic regression model having a random slope (fit using the SAS NLMIXED procedure). These trends are estimated with some error, due to instrument-specific measurement error, making the observed correlation values have some bias toward 0. The accuracy calculations below take this attenuation toward 0 into account.

To select the most promising biomarkers, 95% confidence intervals could be used, and Table 8.4 displays results for the attenuated correlation values. Confidence intervals for the correlations are found using Fisher's Z-

transformation.(141) The table uses the MRI cartilage volume, which has an interclass correlation of 0.92 at the medial tibia,(142) as an example biomarker. Table 8.4 shows various correlation values between time trends in the first column, the attenuated correlation (allowing for measurement error) in the second column,

time trend for	Table 8.4 Precision of attenuated correlations betweenime trend for cartilage volume change and the time trendin log odds of incident symptomatic OA				
True	Attenuated	95% CI for Attenuated			
Correlation	Correlation	Correlation			
0.20	0.196	(0.136, 0.254)			
0.40	0.393	(0.340, 0.444)			
0.60	0.589	(0.548, 0.628)			
0.80	0.786	(0.761, 0.808)			
0.90	0.884	(0.870, 0.897)			

and the 95% confidence interval (CI) for the attenuated correlation in the third column. These results show that correlations with incident OA will be estimated with good precision, having confidence interval widths close to 0.1 for moderate correlation values.

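### Table 8.4 overstates the precision of correlations with incident OA, because it treats each knee's log-odds trend as observed without error

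*Protocol*

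**What the plan says.** Section 8.2.4 defines the endpoint per knee: "incident symptomatic knee OA is defined as the first occurrence in a knee of frequent knee symptoms", together with definite tibiofemoral osteophytes in that knee. For structural biomarkers, full marker data are assumed for "about 300 case knees and 1200 control knees". To evaluate surrogacy for onset, the section suggests correlating the biomarker's time trend with the "time trend in log odds of incident OA from a logistic regression model having a random slope". It allows for instrument measurement error and builds the intervals in Table 8.4 with Fisher's z-transformation. It concludes that "correlations with incident OA will be estimated with good precision, having confidence interval widths close to 0.1" at moderate correlation values.

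Two other places treat outcomes differently. Section 8.2.3 says of the same endpoint: "Time-to-event variables, such as incident symptomatic OA, could be analyzed using the discrete-time Cox proportional hazards model". In section 8.2.5, Table 8.7 attenuates the correlation for error in both the WOMAC outcome and the biomarker.

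**The concern.** A slope correlation has Fisher-z precision only if both slopes are seen, or if the error in each is allowed for. That is workable for WOMAC, which is scored at every annual visit. It is not workable for a first-occurrence endpoint. Section 4.1 states "There will be four annual follow-up visits", so each knee yields one of five results: onset at visit 1, 2, 3 or 4, or no onset. No knee shows a trend in log odds. The model infers one from the assumed distribution of random slopes, and that inference carries far more uncertainty than scanner error does.

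Validating biomarkers as potential surrogates is a principal objective (section 3.0), and Table 8.4 is offered as a basis for choosing the most promising ones. Public data users who plan from it would expect to separate candidate markers more finely than the data allow.

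**Working it through.** **Inputs.** Table 8.4 rows; 300 case and 1,200 control knees; four annual visits; 4-year cumulative incidence of 5.5% (section 8.2.4); WOMAC reliabilities of 0.74 and 0.80 (section 8.2.5). The clustering divisor of 1.4 comes from section 8.2.4: "Using the 0.4 interclass correlation for prevalent symptomatic knee OA in the Framingham cohorts". Applying it to this sample is an assumption here; it gives 1,500/1.4 = 1,071. The protocol does not state the n behind Table 8.4.

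**1. Reproduce the table.** Solve n = 3 + [2 × 1.96 / (atanh(upper) − atanh(lower))]². At true correlation 0.40: atanh(0.444) − atanh(0.340) = 0.4772 − 0.3541 = 0.1231, so n = 3 + (3.92/0.1231)² ≈ 1,017. The five rows give 1,009 to 1,025, and n = 1,020 returns all of them to within 0.001.

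**2. Reproduce the attenuation.** 0.393/0.400 = 0.9825, and the factor is about 0.982 in every row. Squared, that is 0.965 = 0.965 × 1.00. Table 8.7 uses the same 0.965 multiplied by the WOMAC reliability:
- Pain: √(0.965 × 0.74) = 0.845, and 0.845 × 0.40 = 0.338, as tabulated.
- Disability: √(0.965 × 0.80) = 0.879, and 0.879 × 0.40 = 0.351, as tabulated.

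So Table 8.4 gives the outcome trend a reliability of 1. (The text cites 0.92 for cartilage volume, but √0.92 = 0.959 would give 0.384, not 0.393. The source of 0.965 is not stated.)

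**3. A favourable case.** Suppose that having the event is an exact threshold on a latent normal trend, with p = 0.20 and q = 0.80. The biserial standard error is (√(pq)/φ − r²)/√n, where φ = 0.280 is the normal density at the threshold, so √(pq)/φ = 0.4/0.280 = 1.43. At r = 0 the variance ratio to Pearson's is 0.16/0.0784 = 2.04, so intervals are 1.43 times wider. Using the visit of onset as well, with cases split equally over the four visits (an assumption), the ratio is 1.38 at r = 0 and at r = 0.2.

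Widths (2 × 1.96 × SE):

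| True r | Table 8.4 | Biserial, n = 1,071 | Biserial, n = 1,500 (no clustering) |
|---|---|---|---|
| 0.4 | 0.104 | 3.92 × 1.269/32.73 = 0.152 | 3.92 × 1.269/38.73 = 0.128 |
| 0.6 | 0.080 | 3.92 × 1.069/32.73 = 0.128 | 3.92 × 1.069/38.73 = 0.108 |

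**4. The model that the protocol names.** Expected information was computed for a discrete-time logistic model with a random slope, four visits and stopping at first event. The biomarker slope was taken as error-free. Two settings were used: 300:1,200 sampling from 5.5% incidence, and a cohort with 20% events. The SD of the random slope (per year) is assumed. Interval widths at r = 0.4 and 0.6:

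| Slope SD | n = 1,071 | n = 1,500 |
|---|---|---|
| 1.0 | 0.16–0.18 | 0.14–0.15 |
| 0.5 | 0.46–0.66 | 0.38–0.55 |
| 0.25 | above 2 (not identified) | above 2 (not identified) |

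With the slope SD treated as known, widths are 0.13–0.42 at n = 1,071 and 0.11–0.35 at n = 1,500. No scenario reaches the tabulated widths.

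**5. What the sample supports for onset.** Information per SD of a continuous marker is about Npq = 1,500 × 0.2 × 0.8 = 240, and 240/1.4 = 171.4. At 80% power and two-sided 0.05, the detectable hazard ratio is about exp(2.802/√171.4) = exp(0.214) = 1.24.

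**The case against.** The strongest reply is that this is illustrative text. The analysis is put forward as something one might consider, no enrolment target rests on Table 8.4, and sections 8.2.3 and 8.2.4 already name time-to-event models for this endpoint. Table 8.3 also gives detectable effects for the same sample. It back-solves to 159–208 effective cases, which implies about 1.21–1.25 per SD, so a figure of 1.24 mostly restates precision already claimed. All of this stands and limits the harm. It does not rescue the sentence on good precision, which is unconditional.

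Several stronger readings are tempting, and the documents do not support them:
- **That no knee-level trend exists.** In a first-event model the random slope is weakly identified, not absent.
- **That published intervals would be too narrow.** Fisher's z builds the planning table only. A fit of the named mixed model would take its standard errors from the likelihood, and weak identification would show as wide intervals or failure to converge. For comparing correlations, section 8.2.3 names a parametric bootstrap.
- **That 1.4 is a strict lower bound.** Using the visit of onset gives 1.38.
- **That the inflation should be computed at the cohort's event rate.** Table 8.4 concerns the sample with full marker data, where 20% of knees are cases.
- **That the correlation would be unweighted for the case enrichment.** The protocol does not say so, and weighting is commonly left to a statistical analysis plan.

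**Conclusion.** The point holds as an overstatement of planning precision. Table 8.4 is arithmetically consistent with its formula, but the formula gives the outcome trend no error, while the endpoint definition ensures that this error dominates. In the favourable latent-threshold case the intervals are roughly 1.4 times wider at low correlation, or about 0.13–0.15 against 0.104 at a true correlation of 0.4. Under the named model they range from moderately wider to uninformative.

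The direction held in every scenario tried, including a known slope SD, an error-free biomarker and no clustering. The degree rests on assumed slope SDs and, for n = 1,071, on the assumed use of the 1.4 divisor.

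**What to change.** Remove Table 8.4 and the sentence on precision, or recompute both with error in the outcome trend. One way is to simulate the first-event random-slope model over a stated range of slope SDs, giving the n and the biomarker reliability used.

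For onset, state precision as the detectable hazard ratio per SD of biomarker change from the discrete-time model in section 8.2.3. This is about 1.24 for 300 cases and 1,200 controls with the 1.4 divisor, labelled as an approximation. Say plainly that it measures prediction of onset, which differs from the correlated change that section 8.2.3 sets out as the test of surrogacy. Keep slope-correlation precision for repeatedly measured outcomes such as WOMAC, where Table 8.7 already allows for outcome error.

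The cost is one replaced table, some wording and a less favourable precision statement. Data collection and sample size do not change.

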8.2.5 Power for Analyses of Progression Biomarkers

Rates of change in key measures of progression such as WOMAC and especially rates of joint space loss could be speculated, but since it is not known whether the rates of change in OAI subjects will more closely resemble those in a community sample with a mixture of symptomatic and radiographic OA(143) or the higher rates observed in clinical samples,(144, 145) projecting such rates would be speculative. A community sample with symptomatic knee OA will probably be somewhere in between. Moreover, power analysis for progression biomarkers will focus not on detecting loss of joint space or decline in WOMAC scores, but rather on testing correlations between changes in these

^v These calculations utilize the fact when the effects are ratios, and from a statistical point of view handled on the log scale, then the loss in detectable effect size for a change in the effective sample size can be estimated by raising the effect size to a power calculated based on the fact that the detectable effect size is proportional to the square root of the effective sample size.

and other variables. Therefore, power for these analyses are not substantially dependent on the rates of change.

An analysis of predictors of progression of knee OA (called OA progression below) might test the effect of risk factors (dichotomous predictors) on outcome (e.g. change in disability and joint space) in knees with prevalent OA at baseline over the follow-up period using random effects models. Based on the original study goals, there will be an expected 480 subjects with bilateral prevalent knee OA and 320 subjects with prevalent unilateral OA. Allowing for withdrawal from the study and the correlation between knees in the same person, the equivalent of about 620 independent knees with symptomatic OA at baseline will have four years of follow-up and these are used to determine the power for OA progression.

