Published test-retest reliabilities (ICC values) for the WOMAC pain scale are 0.65, 0.74, and 0.90, and values of 0.71, 0.80 and 0.92 for the disability scale. For calculating the attenuated correlation between cartilage volume change and WOMAC change, the moderate ICC values of 0.74 and 0.80 for pain and disability,(43) respectively, as well as the ICC for cartilage volume were used. Table 8.3 shows various true correlation values, the corresponding attenuated correlation, and the 95% confidence interval for the attenuated correlation. For example, if the true correlation between the time trend in WOMAC pain and the time trend in cartilage volume were 0.6, we would expect an attenuated correlation of 0.507 with a 95% confidence interval extending from 0.446 to 0.563. This should allow good discrimination between candidate biomarkers for progression with reasonable levels of correlation with WOMAC scales.

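### Tables 8.4 and 8.7 do not follow from the stated cartilage-volume ICC of 0.92: all 15 rows need about 0.965, so either the stated ICC or both tables need correcting

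*Protocol*

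**What the plan says.** Section 8.2.4 considers the correlation between the time trend in a biomarker and the time trend in the log odds of incident symptomatic OA. It notes that measurement error pulls the observed correlation toward zero and adds: "The accuracy calculations below take this attenuation toward 0 into account". The input for Table 8.4 is: "The table uses the MRI cartilage volume, which has an interclass correlation of 0.92 at the medial tibia". The interval method is given as "Confidence intervals for the correlations are found using Fisher's Z" (transformation). The sample described just before is "image or biochemical marker data would be available from about 300 case knees and 1200 control knees", but no effective sample size is given for the table.

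Section 8.2.5 does the same for cartilage volume against WOMAC pain and disability (Table 8.7). The inputs are: "the moderate ICC values of 0.74 and 0.80 for pain and disability,(43) respectively, as well as the ICC for cartilage volume were used". The sample size comes from earlier in that section: "the equivalent of about 620 independent knees with symptomatic OA at baseline will have four years of follow-up". For a true correlation of 0.6 with WOMAC pain, the text says "we would expect an attenuated correlation of 0.507 with a 95% confidence interval extending from 0.446 to 0.563". That sentence follows a reference to Table 8.3, but the values are those of Table 8.7.

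The only cartilage-volume ICC in the protocol is 0.92.

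**The concern.** The protocol names every reliability needed to rebuild the attenuated correlations, yet the printed values are higher than those inputs give, by the same proportion in both tables. Validating biomarkers and potential surrogates is one of the two principal objectives in section 3.0, and these tables put numbers on the precision available for it. Section 8.2.4 also suggests using such intervals to pick out the most promising biomarkers. In a public resource, outside users who plan their own analyses from these tables cannot tell which figure to trust.

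**Working it through.** **Inputs.** Cartilage ICC 0.92 (8.2.4). WOMAC ICCs 0.74 for pain and 0.80 for disability (8.2.5). Effective n = 620 for Table 8.7 (8.2.5). Effective n for Table 8.4 is not stated.

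**Formulas.** Attenuated r = true r × √(cartilage ICC × ICC of the other measure), with the other ICC set to 1 in Table 8.4. The 95% interval is tanh(atanh(r) ± 1.96/√(n − 3)).

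**Step 1: factors from the stated inputs.**
- Table 8.4: √0.92 = 0.959; printed values imply about 0.982.
- Pain: √(0.92 × 0.74) = 0.825; printed, about 0.845.
- Disability: √(0.92 × 0.80) = 0.858; printed, about 0.879.

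None of the 15 printed correlations is reproduced.

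**Step 2: ICC implied by the printed values.** Divide each printed value (± 0.0005 for rounding) by its true correlation, square, and divide by the other ICC. The range common to all rows of a set is 0.9641–0.9653 (Table 8.4), 0.9649–0.9663 (pain) and 0.9643–0.9653 (disability). All 15 rows together allow only 0.9649–0.9653.

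**Step 3: reproduce the printed figures.** With 0.965, all 15 correlations match to three decimals. For the worked example, 0.6 × √(0.965 × 0.74) = 0.507. With n = 620 the half-width on the z scale is 1.96/√617 = 0.0789, giving (0.446, 0.563) as printed. All ten Table 8.7 intervals match at n = 620. For Table 8.4 the printed widths imply n of about 1,009–1,026. At n = 1,020 four of five intervals match, and both limits of the first row are within 0.001. Dividing 1,500 knees by 1.4 (one plus the between-knee correlation of 0.4 in 8.2.4) gives 1,071, which fits less well.

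**Step 4: other routes from 0.92 to the printed values.**
- Spearman-Brown averaging of 2, 3, 4 or 5 scans gives 0.958, 0.972, 0.979 or 0.983, none of which is 0.965.
- The five-scan value used without the square root matches 11 of 15 rows. It misses four by 0.001, is not the standard formula and is not described.
- Using 0.92, or the product of the ICCs, without a square root matches no row.
- Any measurement error in the Table 8.4 outcome trend would require a cartilage ICC above 0.965.

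**Step 5: values if 0.92 is correct** (n = 1,020 for Table 8.4, 620 for Table 8.7).

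| Set | True r | Printed | With ICC 0.92 |
|---|---|---|---|
| 8.4 | 0.20 | 0.196 (0.136, 0.254) | 0.192 (0.132, 0.250) |
| 8.4 | 0.40 | 0.393 (0.340, 0.444) | 0.384 (0.330, 0.435) |
| 8.4 | 0.60 | 0.589 (0.548, 0.628) | 0.575 (0.533, 0.615) |
| 8.4 | 0.80 | 0.786 (0.761, 0.808) | 0.767 (0.741, 0.791) |
| 8.4 | 0.90 | 0.884 (0.870, 0.897) | 0.863 (0.847, 0.878) |
| 8.7 pain | 0.20 | 0.169 (0.091, 0.244) | 0.165 (0.087, 0.241) |
| 8.7 pain | 0.40 | 0.338 (0.266, 0.406) | 0.330 (0.258, 0.398) |
| 8.7 pain | 0.60 | 0.507 (0.446, 0.563) | 0.495 (0.433, 0.552) |
| 8.7 pain | 0.80 | 0.676 (0.631, 0.717) | 0.660 (0.613, 0.702) |
| 8.7 pain | 0.90 | 0.761 (0.725, 0.792) | 0.743 (0.705, 0.776) |
| 8.7 disability | 0.20 | 0.176 (0.098, 0.251) | 0.172 (0.094, 0.247) |
| 8.7 disability | 0.40 | 0.351 (0.280, 0.419) | 0.343 (0.272, 0.411) |
| 8.7 disability | 0.60 | 0.527 (0.468, 0.582) | 0.515 (0.454, 0.570) |
| 8.7 disability | 0.80 | 0.703 (0.661, 0.741) | 0.686 (0.642, 0.726) |
| 8.7 disability | 0.90 | 0.791 (0.759, 0.819) | 0.772 (0.738, 0.802) |

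The common ratio is √(0.92/0.965) = 0.976, a reduction of about 2.4%.

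**The case against.** The protocol does not print its attenuation formula, so the classical one is an inference. This stands as a caveat only: with a cartilage ICC of 0.965 that formula reproduces every row, and none of the alternatives tried from 0.92 does.

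The tables are offered as examples, and no sample size, power figure or decision rule uses them. That is fair, and it limits the importance of the point. Table 8.7 also rests on the original goal of 800 Progression participants, while Table 4.4 shows 1,330 enrolled. If the effective n scaled in proportion (an assumption), it would be 620 × 1,330/800 ≈ 1,031. The worked example with ICC 0.92 would then have an interval of 0.448 to 0.540, which is narrower than the printed one (0.092 against 0.117).

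The qualitative claims also survive. With 0.92, Table 8.4 widths at true correlations of 0.40 and 0.60 are 0.105 and 0.082, against 0.104 and 0.080 printed, so the description of widths near 0.1 for mid-range values holds. The intervals at 0.80 and 0.90 still do not overlap. A common factor of 0.976 does not reorder candidates that share this reliability.

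A reader might infer that precision has been overstated. The protocol does not support that without a condition: if about 0.965 was the intended reliability, the tables are right and only the quoted ICC is wrong. One value fitting all 15 rows is as compatible with a slip in the text as with an error in the tables.

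**Conclusion.** The mismatch is real and systematic. The stated ICC of 0.92 and the 15 printed rows cannot both be right under the classical attenuation formula. Which of them is the slip cannot be settled from the protocol.

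If 0.92 is correct, the largest change in a correlation is 0.021 (Table 8.4, true 0.90). The change is below 0.01 at true correlations of 0.20 and 0.40. Interval widths grow by about 0.004 at most, for example from 0.027 to 0.031 in that same Table 8.4 row, and from 0.117 to 0.119 in the worked example. If about 0.965 is correct, no table value changes.

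Because 0.863 lies outside the printed interval (0.870, 0.897), a reader might also infer that biomarker selection would be misled. That goes too far: the rows show precision around assumed true correlations, and are not limits within which the study's estimate is predicted to fall.

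The recalculated Table 8.4 intervals rest on the back-solved n of about 1,020. The ICC finding does not, because it uses the point values alone. This is a minor correction.

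**What to change.** Confirm which cartilage-volume reliability was intended, then do one of the following:
- **If 0.92:** recompute the correlations and intervals in Tables 8.4 and 8.7, and change the worked example in 8.2.5 to 0.495 (0.433, 0.552).
- **If about 0.965:** replace 0.92 in 8.2.4 with the value actually used and give its source. The tables and worked example stay as they are.

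In either case, state the attenuation formula and the effective n behind Table 8.4 so that both can be checked. The cost is at most 15 recalculated rows and a few sentences, with no change to design, enrolment or data collection.
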